### ***4. Definitions:***

Difficult IV access patient is defined as failure of 2 attempts to cannulate upper limb veins in patients with invisible or non-palpable veins after application of a tight proximal tourniquet. Successful cannulation is defined as the ability to aspirate blood and ability to flush the cannula without resistance to the flow and without evidence immediate extravasation.

Failure PIVC is defined as extravasation with initial infusion or inability to withdraw blood. Failed cannulation is defined as failed three attempts excluding the initial two attempts which are part of the definition of difficult venous cannulation. Time will be recorded in minutes in real time by the ICU nurse with time zero defined as the first skin puncture after patient randomization in the study.

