### **3.6: *outcome measures:***

#### **Primary outcome measure:**

- Successful cannulation by ICU nurses.

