#### **Secondary outcome measures:**

- Number of punctures attempted.
- 24 hours catheter survival.
- Complications (cellulitis ,phlebitis arterial puncture, nerve injuries, infiltration, hematoma formation).
- Subsequent need for PICC or central line.

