### **3.7. Data collection and processing**

Intensive care nurses participating in the study will record all the data related to outcome measures on a preprinted data collection forms in real time. The raw data will be entered by investigators into SPSS software for analysis.

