### ***3.8. Data analysis***

An intention-to-treat analysis will be performed. Using the power of 80% and alpha of 0.05, the sample size was calculated to be 25 per group. Categorical variables such as success rate, catheter survival rate and complication rate will be presented as a percentage and will be compared using Fisher exact tests. Continuous variables such as insertion time and the number of attempts will be shown as mean, median (with interquartile ranges), and 95% confidence interval (CI) and will be compared using Mann-Whitney U tests. All statistical analysis will be conducted using IBM SPSS Base 25 for Windows.

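### Does the mismatch between the success and failure definitions for a cannula leave the primary outcome or the attempt count undefined?

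*Protocol*

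**What the plan says.** The primary outcome in section 3.6 is "Successful cannulation by ICU nurses". Section 4 gives its meaning: blood can be aspirated, and there is "ability to flush the cannula without resistance to the flow and without evidence immediate extravasation". All three conditions must hold.

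Section 4 then gives two further definitions. At catheter level, "Failure PIVC is defined as extravasation with initial infusion or inability to withdraw blood". At patient level, "Failed cannulation is defined as failed three attempts excluding the initial two attempts which are part of the definition of difficult venous cannulation".

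The secondary outcomes in section 3.6 include "Number of punctures attempted". Section 3.8 states that "An intention-to-treat analysis will be performed", compares success rates by Fisher's exact test, and compares "Continuous variables such as insertion time and the number of attempts" by the Mann-Whitney test. Under section 3.7, "Intensive care nurses participating in the study will record all the data related to outcome measures", in real time on preprinted forms. Section 3.1 says that the trial is not blinded.

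**The concern.** Success and failure of a cannula ought to be complements, and here they are not. Flush resistance appears only on the success side. Extravasation is called immediate in one sentence and tied to the initial infusion in the other.

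Two consequences seem possible. First, some cannulas might have no class, or two classes, in the primary analysis. Second, the limit on attempts might be loose. The success definition contains no limit; the limit appears only in the patient-level definition, as three failed attempts. If the catheter-level failure sentence were the sole test of a failed attempt, a flush-resistant attempt would not use up one of the three. A success at a fourth puncture would then count, and the maximum of the attempt count would differ between readings. Because unblinded nurses record the outcomes, a loose rule would also leave room for judgement.

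**Working it through.** **Step 1: do the definitions cover every case?** Three yes/no checks give 2 × 2 × 2 = 8 combinations. Treat the two extravasation wordings as the same check.

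| Blood return | Free flush | Extravasation | Class |
|---|---|---|---|
| yes | yes | no | success |
| yes | no | no | neither |
| yes | yes | yes | failure |
| yes | no | yes | failure |
| no | yes or no | yes or no | failure (4 combinations) |

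The split is 1 success, 6 failures and 1 unclassified, with no overlap. If the two extravasation wordings mean different moments, a cannula that passes the flush and then leaks at the first infusion would meet both definitions.

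**Step 2: which term does each analysis use?**

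- Primary outcome: the success definition. The unclassified row is not a success, so it falls in the non-success column of the Fisher table. The failure sentence is not needed.
- Number of punctures: every skin puncture counts, whatever happens at the flush. Only the maximum could depend on the reading.
- 24-hour catheter survival, complications, and later need for a PICC or central line: none is defined through the catheter-level failure sentence.

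**Step 3: how large would the strained reading be?** The Protocol gives no rate of flush resistance and no design success rates, so every input here is an assumption. The 76% and 56% come from an emergency department trial cited in section 2. They are treated as success within three independent attempts, with 25 patients per arm (section 3.8).

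The per-attempt probability of no success is q = (1 − success)^(1/3):

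- ultrasound: 0.24^(1/3) = 0.6214
- landmark: 0.44^(1/3) = 0.7606

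If every unsuccessful attempt counts, success is 1 − q³ = 0.76 and 0.56. If a share r of attempts aspirate but resist the flush and are not counted, success becomes 1 − ((q − r)/(1 − r))³. For r = 0.10 in the ultrasound arm, (0.6214 − 0.10)/0.90 = 0.5794 and 1 − 0.5794³ = 0.8055.

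| r, both arms | Ultrasound | Landmark | Difference (points) | Extra successes per 25 | Fisher power |
|---|---|---|---|---|---|
| 0 | 76.0% | 56.0% | 20.0 | none | 22.8% |
| 2% | 76.9% | 56.8% | 20.0 | 0.22 and 0.21 | 22.9% |
| 5% | 78.2% | 58.2% | 20.1 | 0.56 and 0.54 | 23.1% |
| 10% | 80.6% | 60.5% | 20.1 | 1.14 and 1.11 | 23.4% |

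Power is that of the two-sided exact test at 0.05 in favour of ultrasound, by full enumeration of both binomials. It serves only to compare the two readings; it is no verdict on the sample size, since 76% and 56% are not stated as design rates. Differences are taken before rounding: at r = 10%, 80.55 − 60.46 = 20.1. Even then the treatment difference hardly moves, and power rises by 23.4 − 22.8 = 0.6 percentage points.

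**The case for a change.** The best case for a change is that this is stated text in conflict with itself, not detail left to a later plan. The Protocol chose to define both terms, one of eight combinations falls between them, and a second overlap arises if the extravasation wordings mean different moments. The only sentence saying what makes a cannula fail omits flush resistance, so the three-attempt limit rests on inference. Nurses who know the allocation apply it at the bedside. Two sentences and one form field would settle it, with no effect on the sample size or the test.

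The description of the text stands, and an editor could tidy it at little cost. The consequence does not stand. The patient-level definition speaks of failed attempts without pointing to the catheter-level failure term. With success fully specified just before it, a failed attempt is most naturally one that did not succeed. A fourth puncture arises only if the failure sentence is imported as the exclusive test. The extravasation wordings most plausibly describe one early check on the new cannula. An effect confined to one arm would matter more, but nothing in the Protocol suggests one.

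**Conclusion.** The mismatch in section 4 is a clerical slip, and no change to the plan follows. The primary analysis compares success with non-success among all randomised patients, and the success definition alone is enough to classify each of them. Every puncture is counted on either reading. Under the strained reading, with up to 10% flush-resistant attempts in both arms, the shift is about 1.1 patients per arm, 0.1 points in the treatment difference and 0.6 points in power.

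These figures rest on assumed resistance rates, independent attempts, literature success rates and equal effect in both arms. The conclusion does not depend on them: it rests on the analyses using the success definition and not the failure sentence. It does assume that nurses and analysts treat any attempt short of success as a failed attempt, and that both extravasation wordings mean the same check. Both are the ordinary reading of the section.

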# ***Ultrasound-guided peripheral IV vs. standard technique in difficult vascular access patients by ICU nurses.***

## ***“Research Protocol”***

### ***1-Introduction:***

Peripheral intravenous access is one of the most common and most important invasive procedure performed by ICU nurses. The importance of being able to insert an IV quickly, successfully and with little discomfort cannot be overestimated. Establishing good peripheral access is essential in ICU because this allows timely administration of fluid and medication and also allow early discontinuation or even avoidance of central line when there are no specific indications for their use.

Failure in establishing good peripheral access is a very frequent problem in ICU because of the high prevalence of chronic illness, peripheral edema, obesity and for many other reasons. Multiple attempts in establishing IV access in difficult IV access (DIVA) patients frequently lead to a high level of patient discomfort and nurse's frustration. Peripheral IV cannulation can be incredibly time intensive for nurses when patients are DIVA. Furthermore, failure of peripheral intravenous cannulation (PIVC) in ICU setting frequently leads to insertion of a central line or PICC which are associated with more risk of catheter-associated infection and other serious complications [1].

Using Ultrasound to guide central line insertion is the standard of care but ultrasound-guided PIVC in difficult patients remained poorly utilized rescue tool despite its potential advantages in the ICU setting. Ultrasonographic guidance may improve the rate of successful PIVC in patients who have been historically difficult to access, leading to less time spent obtaining intravenous access and greater patient satisfaction.

In difficult IV access patients, we hypothesize that ultrasound-guided peripheral intravenous cannulation (USG-PIVC) increases the success rate of peripheral IV access in difficult IV access ICU patients. In addition, we hypothesize the USG-PIVC is a very safe procedure and is associated with very few minor complications.

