In another small randomized prospective study conducted in an emergency department in 2005, Costantino et al found that ultrasound-guided IV cannulation performed by emergency physicians are more successful than traditional “blind” techniques, requires less time, decreases the number of percutaneous punctures, and improves patient satisfaction in patients with difficult I.V access [7]. In a recent single-center randomized prospective study in ED, nurses were found to be more successful in obtaining IV access using US guidance than palpation technique in difficult access patients. Nurses using US-guided technique had a higher success rate of 76% in placing a functional IV compared to 56% using the standard palpation technique [8].

In a single-center retrospective study, a single physician attempt in placing peripheral IVs using ultrasound in difficult cannulation ICU patients found that first attempt success rate was 77% with 99% overall success rate. As a result of placing these PIV catheters, 40 central lines were discontinued, and 34 central lines were avoided. This study has a limitation because it is a retrospective study examining a single physician's experience with the technique [9]. In another

small ICU RCT, the ultrasound-guidance technique was more successful without increasing cannulation time despite the use of additional equipment [10].

In a recent systematic review published in 2016, the authors found that the ultrasound-guided technique improves the success rate of intravenous access significantly (OR = 3.00, p < .0001) and decreased the number of attempts in the overall group of difficult intravenous-access patients [11].

Ultrasound-guided peripheral IV cannulation has a steep learning curve. Stoltz La found that new learners of the procedure are capable of a greater than 70% success rate after placement of four USG PIVCs. A success rate of greater than 88% is achieved after 15 to 26 attempts [12]

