### ***3.5. Study procedure***

The study will be conducted in two phases. Phase one will involve education and training of a cohort of nurses to perform US-guided PIVC. Experienced ICU nurses with two years of experience will be recruited to participate in the study. All nurses will have no prior experience in USG-PIVC prior to this study. Education consists of didactic two hours lecture and hands-on practice on synthetic training models (blue phantoms). This will cover basic machine operation, image optimization, sonographic anatomy and ultrasound techniques for guiding PIVC. This will be followed by 2-3 months observation period during which nurses have to perform at least 15 successful ultrasound-guided PIVC on live subjects before actual patients' enrolment. Phase two involved patient enrolment of difficult peripheral access ICU patients meeting specific inclusion and exclusion criteria. Patients will be systematically randomized to the ultrasound-guided or the landmark technique (control) using envelop randomization.

Only upper limb veins will be selected for cannulation. All the cannulation will be done under semi aseptic technique as per standard PIV placement and cleaning procedures. USG-PIVC will be performed using sterile gel for the

procedure, and the ultrasound probe will be covered with sterile adhesive films (e.g., 3M Tegaderm). Two already available departmental ultrasound machines (sonosite edge ) will be used for this study. High-frequency probe (5-10 MHz) with single operator out of plane (short access) approach will be used for ultrasound-guided cannulation.

When using USG-PIVC, veins deeper than 1.5 cm from the skin surface and veins with diameter less than 0.3 cm will be avoided because of high failure rate and increased risk of extravasation. Catheter length and size will be selected based on the depth and size of veins to ensure that a sufficient portion of the catheter will remain in the vessel to prevent early failure.

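### Insertion time starts at first skin puncture, so extra ultrasound preparation goes uncounted and the comparison, read as time to obtain access, leans toward ultrasound

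*Protocol*

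**What the plan says.** Section 4 (Definitions) sets the clock for both arms: "Time will be recorded in minutes in real time by the ICU nurse with time zero defined as the first skin puncture", counted after randomization. Section 3.8 (Data analysis) makes the result a comparison: "Continuous variables such as insertion time and the number of attempts will be shown as mean", with median and confidence interval, tested by Mann-Whitney U.

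Section 3.5 (Study procedure) describes the work that precedes a puncture. Some of it is shared: "All the cannulation will be done under semi aseptic technique as per standard PIV placement and cleaning procedures". Some belongs to the ultrasound arm only: sterile gel is used, "the ultrasound probe will be covered with sterile adhesive films", and "veins deeper than 1.5 cm from the skin surface and veins with diameter less than 0.3 cm will be avoided", so depth and diameter have to be judged on the screen before the needle goes in.

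Two other places show why time is of interest. The introduction suggests that ultrasound may raise the success rate, "leading to less time spent obtaining intravenous access and greater patient satisfaction". The literature review cites an ICU trial in which ultrasound was "more successful without increasing cannulation time despite the use of additional equipment".

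Insertion time is not a listed outcome in section 3.6. The nearest listed item is "Number of punctures attempted". No section calls for an earlier start time to be recorded.

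**The concern.** The clock starts after the ultrasound-specific work for the first attempt is done. If that work takes longer than the landmark arm's inspection and palpation, the excess disappears from the ultrasound arm's time and the comparison moves toward ultrasound.

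Two wrong readings become possible. Equal total times can look like an ultrasound advantage, and a truly longer ultrasound procedure can look like no difference. Both bear on the practical question for an ICU, which is whether the extra equipment costs nurses time.

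The stakes are limited. The primary outcome is cannulation success, which does not depend on the clock. But the protocol plans a between-arm test of this variable and fixes its start point, so a later analysis plan could not repair it from the data collected.

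**Working it through.** **Inputs from the protocol.** Time zero is first skin puncture (section 4). The test is Mann-Whitney U, with 25 per group and alpha 0.05 (section 3.8). Ultrasound-only preparation is described in section 3.5. The protocol gives no durations, so there is no time figure to reproduce.

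**Which work is counted**

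| Work | Arm | On the clock? |
|---|---|---|
| Skin cleaning before first attempt | both | no |
| Inspection and palpation before first attempt | landmark | no |
| Gel, probe cover, scanning for a suitable vein before first attempt | ultrasound | no |
| Re-scanning or renewed search before later attempts | each arm | yes |
| Repeat punctures | both | yes |

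Shared preparation cancels in the difference. Only the excess of ultrasound over landmark preparation before the first puncture matters.

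**Identity.** For each arm, total access time = preparation + time from first puncture. Write E for mean ultrasound preparation minus mean landmark preparation. Then, for mean times:

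recorded difference (ultrasound minus landmark) = total difference − E.

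- Total times equal and E = 3 min: recorded difference = 0 − 3 = −3 min, an apparent ultrasound advantage.
- Recorded difference 0 and E = 3 min: total difference = 0 + 3 = +3 min, a real delay that is not seen.
- E = 0: no shift. E negative: the shift favours landmark.

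**Illustration of size (all time inputs are assumptions).** Total times are lognormal and identical in both arms, with 25 per arm. E minutes are subtracted from the ultrasound arm, and times are rounded to whole minutes with a minimum of 1. The test is a two-sided Mann-Whitney at 0.05, counted when significant in favour of ultrasound, over 10,000 trials per scenario. The simulation standard error is at most √(0.5 × 0.5 / 10,000) = 0.5 percentage points.

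| Median (min) / log-SD | E = 0 | 1 | 2 | 3 | 4 |
|---|---|---|---|---|---|
| 8 / 0.5 | 2.3% | 13.6% | 41.6% | 73.7% | 92.0% |
| 8 / 0.8 | 2.2% | 8.4% | 21.4% | 41.2% | 61.9% |
| 15 / 0.8 | 2.4% | 5.2% | 9.2% | 15.2% | 25.7% |
| 20 / 0.5 | 2.5% | 5.4% | 10.7% | 18.7% | 29.5% |
| 20 / 0.8 | 2.2% | 4.1% | 7.3% | 10.4% | 16.0% |

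**Mirror case.** Times after first puncture are equal, and the ultrasound total is truly 1, 2, 3 or 4 min longer. A common earlier start finds ultrasound slower in 13.9%, 42.1%, 73.6% and 92.7% of trials (8 / 0.5), or 4.2%, 6.3%, 10.8% and 16.4% (20 / 0.8). The puncture clock finds it slower in 2.1% to 2.6%, the chance rate.

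**Second model, set up the other way.** Time from first puncture is lognormal with log-SD 0.7, median 3 min with ultrasound and 5 min with landmark, over 4,000 trials. The puncture clock significantly favours ultrasound in about 67% to 70% of trials whatever E is. Counting the excess preparation, this falls to about 18%, 2% and 0.1% at E = 1, 2 and 3 min.

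**The case against.** The strongest reply is that time from first puncture is a legitimate measure, defined explicitly and identically for both arms. The protocol nowhere says the result will be read as total time. The stated hypotheses concern success and safety, and the introduction's remark on time is hedged background. That stands: there is an error only if the result is read as time to obtain access. But this is the only benefit in time that the protocol mentions, and nothing in section 3.8 or 4 guards against the reading.

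Second, the sign of the excess is assumed. These patients have poor veins and two failed attempts behind them, so the landmark search may also be long. That stands too. The excess could be zero or negative, which would remove or reverse the shift, and the planned data would not show which.

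Third, the percentages rest on invented distributions. The largest comes from a strained corner: at median 8 min and log-SD 0.5, a total below 4 min has probability Φ(ln 0.5 / 0.5) = Φ(−1.39), about 8%, so some simulated patients finish in less than their excess preparation. With log-SD 0.8 it is about 19%. The mirror case is close to true by construction. The figures show that the effect can be material; they do not estimate it.

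Fourth, the cited ICU trial's start point is not given, so that trial is no benchmark. Agreed: it shows only that added procedure time is a question the protocol raises.

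Fifth, insertion time is not a listed outcome. That limits the weight of the point but does not remove the planned test.

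**Conclusion.** The concern holds in its conditional form. Whenever ultrasound preparation before the first puncture takes longer than landmark preparation, the planned comparison, read as time to obtain access, is shifted toward ultrasound by that excess. The direction follows from the definitions. The amount cannot be known from the protocol. In the equal-total-time illustrations, 1 to 4 excess minutes give a significant ultrasound advantage in anything from 4% to 92% of trials, depending on the assumed median, spread and excess.

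This is a minor to moderate point. It concerns an unlisted but tested variable and leaves the primary outcome untouched. It should still be corrected before enrolment.

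**What to change.** In section 4, define a start time common to both arms and taken before any preparation, and use it for the between-arm comparison in section 3.8. Either envelope opening or the start of preparation at the bedside will serve. The second excludes delays such as fetching a machine. State which is used. Keep first puncture as a second stamp and report that interval descriptively, labelled as time from first puncture.

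The cost is one extra field on the preprinted form that nurses already complete in real time, and no information is lost. The ultrasound time result may look less favourable, and with envelope opening as the start it will include some logistics delay.

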## **5. Ethical considerations:**

The course of research ethics (CORE) will be completed by the researchers, and the study proposal will be submitted for approval to the Queen's university health sciences research ethics board (HSREB). For this research project, we will request to waive the informed consent because the intervention involves no more than minimal risk to patients. Peripheral IV insertion is a minor common procedure, and it is usually conducted by ICU nurses without any form of consenting in intubated ICU patients. It is an essential intervention and part of the standard of care that carries minimal risk. In addition, It is difficult to carry out this research with informed consent because this might affect recruitment and feasibility of this study in the ICU setting. The waiver or alteration will not adversely affect the rights and welfare of patients. Patients' confidentiality will be protected per the Tri-Council Policy Statement: Ethical Conduct for Research Involving Humans. The researchers will follow the code of best practices in research and declare no conflicts of interest that could affect the outcome of the study.

